# 7.5. Pharmacodynamic Analysis

Analyses of secondary endpoints relating to 24-hour urinary oxalate corrected for BSA and 24-hour urinary oxalate: creatinine levels are described in Section 7.2 and Section 7.3. Analyses of exploratory PD endpoints (urinary oxalate: creatinine ratios as assessed in random spots, plasma glycolate, 24-hour urinary glycolate: creatinine ratio, and urinary glycolate: creatinine ratios as assessed in random spots) are described in Section 7.4.

### 7.6. Pharmacokinetic Analysis

Pharmacokinetic analyses will be conducted using noncompartmental methods. PK parameters will be calculated using a validated version of Phoenix® WinNonlin.

Population PK analysis is planned for all patients in the study and will be described in a separate population PK analysis plan.

# 7.7. Safety Analyses

Primary safety analyses will compare lumasiran versus placebo during the DB period using the Safety Analysis Set. Long-term safety analyses of lumasiran will be summarized by treatment sequence (lumasiran/lumasiran, placebo/lumasiran, all treated arm) using the All Lumasiran Treated Set.

The safety analyses will be based upon treatment received (i.e. if a patient receives at least one dose of lumasiran, then he/she will be included in the lumasiran arm).

The primary safety parameter is treatment emergent Adverse Event (AEs) which will be defined as an AE that occurs or worsens on or after the first dose date/time of study drug though 84 days after the last dose of study drug. In addition, any AE that worsened in intensity or was subsequently considered related to study drug will be considered treatment emergent. Other safety parameters will include vital signs, ECGs, clinical laboratory assessments and physical exams.

#### 7.7.1. Adverse Events

AEs will be classified using the Medical Dictionary for Regulatory Activities (MedDRA Version 21.1 or later) and displayed in tables using System Organ Class (SOC) and Preferred Terms (PT). All treatment emergent AEs hereafter will be referred to as AEs in this document.

An overview table of AEs will be tabulated. The overview table will include the number and percentage of patients in following categories such as, but not limited to:

- At least 1 AE
- At least 1 drug related AE
- At least 1 severe AE
- At least 1 drug related severe AE
- At least 1 Serious Adverse Event (SAE)
- At least 1 drug related SAE
- At least 1 AE leading to treatment discontinuation
- At least 1 drug related AE leading to treatment discontinuation
- At least 1 AE leading to study withdrawal
- At least 1 drug related AE leading to study withdrawal
- Death

Tabulations by System Organ Class (SOC) and Preferred Term (PT) displaying the number of patients (percentage) and total events will be produced for the following tables:

- All AEs
- Severe AEs
- AEs by Maximum Severity
- AE related to treatment
- AEs related to treatment by Maximum Severity
- All SAEs
- SAEs related to treatment
- AEs leading to treatment discontinuation
- AEs leading to treatment interruption
- AEs leading to withdrawal

Tabulations by PT in decreasing order in frequency within the lumasiran arm will be generated for the following tables:

- All AEs
- All SAEs
- AEs related to treatment
- SAEs related to treatment

There will also be an All AE table generated displaying rates of adverse events adjusted for exposure-time during the respective period.

AE and SAE tables will be generated for each of the following subgroups: Age, Gender, Race, and eGFR categories.

Patients who report multiple occurrences of the same AE (preferred term) will be classified according to the most severe occurrence or most related.

Separate listings will be provided for deaths, SAEs, and AEs leading to discontinuation of study drug, withdrawal of study drug and/or dose interruption. By-subject AE listings will be provided.

Additional summaries of other Standardised MedDRA Queries (SMQs) or adverse event grouping may be summarized such as but not limited to the following:

**Injection Site Reactions [ISRs]**: AEs mapping to the High-Level Term (HLT)=" Injection Site Reactions" using MedDRA dictionary will be included in the summary. Frequency (percentages) of ISRs by HLT and PT will be generated. A separate listing will be generated to display all patients who reported ISRs.

A table will also be generated to display the number of patients with at least 1 ISR, total number of doses (any dose split into multiple injections will be considered 1 dose in summary), total number of doses with ISRs, and the signs and symptoms reported due to ISRs. If there are multiple ISRs that occur in between two consecutive injections, then these events will be considered as 1 ISR and considered related to the earlier injection.

**Hepatic AEs, including AEs of LFT abnormalities**: These AEs are mapped to the Standardized MedDRA Query (SMQ) drug-related hepatic disorders - comprehensive search (includes all narrow and broad terms). Frequency (percentages) of drug-related hepatic disorders will be summarized by SOC and PT. A separate listing will be generated of all patients reporting these events.

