6.5.7. Adverse Events

6.5.7.1. Definitions

Adverse Event

According to the International Council on Harmonisation (ICH) E2A guideline Definitions and Standards for Expedited Reporting, and 21 CFR 312.32, IND Safety Reporting, an adverse event (AE) is any untoward medical occurrence in a patient or clinical investigational subject administered a medicinal product and which does not necessarily have a causal relationship with this treatment.

Renal stone events (as defined in Section 6.3.3) are recorded for efficacy assessment of lumasiran. These events will not be treated as AEs or SAEs. Other AEs or SAEs occurring during a renal stone event are reported.

Serious Adverse Event

A serious adverse event (SAE) is any untoward medical occurrence that at any dose:

- Results in death
- Is life-threatening (an event which places the patient at immediate risk of death from the event as it occurred. It does not include an event that had it occurred in a more severe form might have caused death)
- Requires in-patient hospitalization or prolongation of existing hospitalization
- Results in persistent or significant disability or incapacity
- Is a congenital anomaly or birth defect
- Is an important medical event that may not be immediately life-threatening or result in death or hospitalization but may jeopardize the patient and may require intervention to prevent one of the other outcomes listed in the definition above (eg, events include allergic bronchospasm requiring intensive treatment in an emergency room or at home, blood dyscrasias, convulsions, or the development of drug dependency or abuse).

Adverse Events of Clinical Interest

The following are considered to be AEs of clinical interest:

- Alanine aminotransferase (ALT) or aspartate aminotransferase (AST) $>3\times$ upper limit of normal (ULN)
- Severe or serious injection site reactions (ISRs); ISRs that are associated with a recall phenomenon (reaction at the site of a prior injection with subsequent injections), or those that lead to temporary dose interruption or permanent discontinuation of study drug.

An ISR is defined as a local reaction at or near the site of injection. “At or near” the injection site includes reactions at the injection site, adjacent to the injection site, or a reaction which may shift slightly away from the injection site due to gravity (eg, as may occur with swelling or hematoma). Reactions with onset and resolution within

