4 hours of the injection (eg, transient pain/burning at injection site) do not meet the study definition of ISRs, unless immediate treatment is required. A systemic reaction which includes the injection site, eg, generalized urticaria, other distinct entities or conditions like lymphadenopathy that may be near the injection site is not considered an ISR.

For information on recording and reporting of AEs of clinical interest, see Section [6.5.7.2](#) and Section [6.5.7.3](#), respectively.

Adverse Event Severity

Adverse events are to be graded according to the categories detailed below:

Mild:	Mild; asymptomatic or mild symptoms; clinical or diagnostic observations only; intervention not indicated.
Moderate:	Moderate; minimal, local or noninvasive intervention indicated; limiting age appropriate instrumental activities of daily living (eg, preparing meals, shopping for groceries or clothes, using the telephone, managing money).
Severe:	Severe or medically significant but not immediately life-threatening; hospitalization or prolongation of hospitalization indicated; disabling; limiting self-care activities of daily living (ie, bathing, dressing and undressing, feeding self, using the toilet, taking medications, and not bedridden); OR life-threatening consequences; urgent intervention indicated; OR death related to an adverse event.

Changes in severity should be documented in the medical record to allow assessment of the duration of the event at each level of severity. Adverse events characterized as intermittent require documentation of the start and stop of each incidence. When changes in the severity of an AE occur more frequently than once a day, the maximum severity for the experience that day should be noted. If the severity category changes over a number of days, then those changes should be recorded separately (with distinct onset dates).

AE severity and seriousness are assessed independently. ‘Severity’ characterizes the intensity of an AE. ‘Serious’ is a regulatory definition and serves as a guide to the Sponsor for defining regulatory reporting obligations (see definition for SAE).

Relationship of the Adverse Event to Study Drug

The relationship of each AE to study drug should be evaluated by the Investigator by a “yes” or “no” response to the question: “Is there a reasonable possibility that the event may have been caused by the study drug?” A “yes” response indicates that the event is considered as related to the study drug.

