6.5.7.2. Eliciting and Recording Adverse Events

Eliciting Adverse Events

The patient and legal guardian, if applicable, should be asked about medically relevant changes in the patient’s health since the last visit. The patient and legal guardian, if applicable, should also be asked if the patient has been hospitalized, had any accidents, used any new medications,

or changed concomitant medication routines (both prescription and over-the-counter). In addition to patient observations, AEs will be documented from any clinically relevant laboratory findings, physical examination findings, ECG changes, or other findings that are relevant to patient safety.

Recording Adverse Events

The Investigator is responsible for recording non-serious AEs that are observed or reported by the patient after administration of the first dose of study drug regardless of their relationship to study drug through the end of study. Non-serious AEs will be followed until the end of study.

The Investigator is responsible for recording SAEs that are observed or reported by the patient after the time when the informed consent is signed regardless of their relationship to study drug through the end of study. SAEs will be followed until satisfactory resolution, until baseline level is reached, or until the SAE is considered by the Investigator to be chronic or the patient is stable, as appropriate.

All AEs must be recorded in the source records for the clinical study center and in the eCRF for the patient, whether or not they are considered to be drug-related. Each AE must be described in detail: onset time and date, description of event, severity, relationship to study drug, action taken, and outcome (including time and date of resolution, if applicable).

For SAEs, record the event(s) in both the eCRF and the SAE form.

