6.5.7.3. Reporting Adverse Events of Clinical Interest to Sponsor/Designee

For AEs that are considered AEs of clinical interest (Section 6.5.7.1), the Sponsor or its designee should be notified within 24 hours using a supplemental AEs of Clinical Interest eCRF.

Additional clinical and laboratory information may be collected. Refer to CRF completion guidelines for details on reporting events in the supplemental AEs of Clinical Interest eCRF.

For all ISRs, the Investigator, or delegate, should submit a supplemental ISR eCRF, recording additional information (eg, descriptions, onset and resolution date, severity, treatment given, event outcome).

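### SAP 7.7.1 identifies injection site reactions by MedDRA high-level term without applying the protocol's study definition, so the ISR counts can include reactions the protocol excludes and miss some it includes.

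*SAP*

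**What the plan says.** **Protocol 6.5.7.1 (Definitions)** sets out what counts: "An ISR is defined as a local reaction at or near the site of injection". Adjacent reactions, and those that shift slightly through gravity, are included. Two groups are then removed.

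- Short-lived reactions: "Reactions with onset and resolution within" 4 hours of the injection "do not meet the study definition of ISRs, unless immediate treatment is required".
- Systemic reactions that include the injection site, and "other distinct entities or conditions like lymphadenopathy that may be near the injection site is not considered an ISR".

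**Protocol 6.5.7.2** covers AEs in general: "The Investigator is responsible for recording non-serious AEs that are observed or reported by the patient" after the first dose. Each AE record is to carry the time and date of onset and, where applicable, of resolution.

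**Protocol 6.5.7.3** adds a dedicated form: "For all ISRs, the Investigator, or delegate, should submit a supplemental ISR eCRF".

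**SAP 7.7.1** introduces its ISR and hepatic groupings with "Additional summaries of other Standardised MedDRA Queries (SMQs) or adverse event grouping may be summarized". For ISRs, the AEs that map to the HLT Injection Site Reactions "using MedDRA dictionary will be included in the summary". It then plans a listing of patients with ISRs, and a table of patients with at least one ISR, total doses, doses with ISRs, and signs and symptoms. Several ISRs between two consecutive injections count as one. The SAP does not name the supplemental ISR eCRF, and it gives the patient and dose table no definition or data source of its own.

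**The concern.** The protocol and the SAP use the same label for two different sets of events. A brief burning sensation that needs no treatment is not an ISR under the protocol. If the site records it as an AE and it codes to the HLT, it is an ISR in the SAP's tables. In the other direction, a swelling or hematoma near the injection site is an ISR under the protocol. If its reported term does not point to the injection site, it may code elsewhere and drop out.

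Protocol 1.5 names ISRs as one of two important potential risks of lumasiran, the other being liver function test abnormalities. A reader who takes the ISR patient count, or the count of doses with ISRs, to follow the protocol's definition would be misinformed, and nothing in the SAP warns of this. In a trial of 30 patients, one or two reclassified patients visibly change a percentage.

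**Working it through.** No ISR rate or expected count appears in either document, so there is no plan figure to reproduce. The check compares the texts and then shows how sensitive the counts are.

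**Step 1. The two definitions side by side**

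| Feature | Protocol 6.5.7.1 | SAP 7.7.1 |
|---|---|---|
| Basis | Local reaction at or near the site | AE coded to the HLT |
| Onset and resolution within 4 hours, untreated | Not an ISR | Counted if recorded as an AE and coded to the HLT |
| Onset and resolution within 4 hours, immediate treatment needed | ISR | Counted if coded to the HLT |
| Systemic reaction or distinct nearby condition | Not an ISR | Decided by coding alone |
| Adjacent or gravity-shifted reaction | ISR | Counted only if coded to the HLT |
| Dedicated data source | Supplemental ISR eCRF (6.5.7.3) | Not mentioned |

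**Step 2. Can an excluded reaction reach the SAP table?** Yes, if it is recorded and coded that way. Failing the ISR definition does not stop an event being an AE. Where the protocol wants events kept out of AE reporting it says so, as it does for renal stone events in 6.3.3 and 6.5.7.1. It gives no such exemption to short-lived injection reactions. Protocol 1.5 says mild, transient ISRs were seen in Phase 1, but not how many resolved within 4 hours.

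**Step 3. Is the difference declared?** SAP Section 1 says changes to the protocol's analysis methods will be described in Section 8. Section 8 says nothing about ISRs. For renal stone events, by contrast, SAP 7.4 repeats the protocol's definition.

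**Step 4. Weight of one patient.** Inputs: 30 planned patients (Protocol 3.4), randomized 2:1 (Protocol 3.5).

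- Lumasiran: 30 × 2/3 = 20; one patient = 1/20 = 5 percentage points.
- Placebo: 30 × 1/3 = 10; one patient = 1/10 = 10 percentage points.

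A patient whose only reaction was transient and untreated raises that arm's rate by this amount. A protocol ISR patient missed by coding lowers it by the same amount. Suppose 4 lumasiran patients met the protocol definition (assumed), 4/20 = 20%. Adding 1, 2 or 4 transient-only patients gives 5/20 = 25%, 6/20 = 30% or 8/20 = 40%.

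**Step 5. Per-dose count.** Double-blind doses fall at Day 1 and Months 1, 2 and 3 (Protocol 5.2.2), so 20 × 4 = 80 lumasiran doses. Assume 10% of doses (8) have a protocol ISR and 5% to 15% (4 to 12) have a recorded untreated reaction under 4 hours. Neither rate comes from the documents.

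| Overlap between the two kinds of dose | 4 transient doses | 12 transient doses |
|---|---|---|
| None | (8 + 4)/80 = 15% | (8 + 12)/80 = 25% |
| As much as possible | 8/80 = 10% | 12/80 = 15% |

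An assumed protocol rate of 10% would thus appear as anything from 10% (no change) to 25%. Overlap matters because the SAP counts doses with ISRs and merges reactions between injections.

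**The case against.** The best defence is that the SAP breaks no stated analysis rule. The definition in Protocol 6.5.7.1 stands under adverse events of clinical interest, which that section ties to recording and reporting. Protocol 7.2.8 says AEs are coded in MedDRA and summarized by class and term, and leaves other safety summaries to the SAP. A broad MedDRA grouping is a normal safety choice. SAP 7.7.1 does the same for hepatic events, and the rule applies equally to both arms of a blinded comparison. AE times are recorded and listings are planned, so short reactions could be found afterwards.

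Much of this stands. The HLT count is legitimate and should stay. What it does not answer is the label: the protocol speaks of a study definition of ISRs, and the SAP uses the same name for a different set without saying so. Listings let a reader reconstruct the protocol count, but no planned table states it.

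A reader might infer more than the documents support:

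- **That a headline tolerability result is wrong.** The primary safety parameter is the frequency and seriousness of AEs overall (SAP 3.2.4). ISRs are not among the listed AE overview categories, and the ISR summary comes under wording that makes it optional.
- **That transient reactions will certainly be counted.** This depends on sites recording them as AEs and on how they are coded.
- **That one table mixes two definitions.** The SAP does not state the source of the patient and dose table. It might come from the ISR eCRF, whose full content is not shown.
- **That the rate would necessarily be inflated.** Missed cases work the other way, and with overlap the per-dose rate need not move.

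**Conclusion.** The point holds as a mismatch of definitions. As written, SAP 7.7.1 does not apply the protocol's ISR definition and does not tell the reader so. Its ISR patient and per-dose counts can include untreated reactions that start and resolve within 4 hours, and can omit protocol ISRs coded outside the HLT.

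The net size and direction, and the effect on the difference between arms, cannot be determined from the documents. What can be stated is the sensitivity: 5 points per reclassified lumasiran patient and 10 per placebo patient, assuming the planned 20:10 split is achieved. The per-dose range is only an illustration on assumed rates. The primary safety parameter and the efficacy analyses are unaffected. The change is worth making because ISRs are a named important potential risk and the remedy is small.

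**What to change.** In SAP 7.7.1:

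1. Report the ISR patient and per-dose tables under the definition in Protocol 6.5.7.1, including its exception for reactions needing immediate treatment. Identify cases from the supplemental ISR eCRF, cross-checked against onset and resolution times in the AE record. The cross-check is needed because cases defined by the form alone would be lost whenever a form was not submitted. It must use the AE record because Protocol 6.5.7.3 gives onset and resolution date as examples of what the ISR form holds, and a date cannot settle a 4-hour rule.
2. Report the HLT-based count alongside, labelled as a broader MedDRA summary.
3. State the definition and data source under each ISR table.
4. List the AEs on which the two definitions disagree.
5. Record the difference and its reason in SAP Section 8.

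The cost is SAP wording, a derived flag, one extra table and one listing. No new data collection is needed, since the ISR form and the AE times are already required by the protocol.

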### 7.7.2. Clinical Laboratory Data

Clinical laboratory parameters will be expressed in Standard International (SI) units. Laboratory data collected and recorded below lower limit of quantification (LLQ) will be set to the lower limit of detection for calculation of summary statistics. Summaries will only include data from central laboratory. eGFR will not be reported in this section, as this is summarized in the efficacy section. For any local collections of LFTs, these will be included in a separate data listing. Key laboratory parameters will be graded according to NCI CTCAE v5.0.

Summaries for each lab parameter (hematology, chemistry, liver function tests, coagulation and urinalysis), which are continuous variables, will have a tabular summary of descriptive statistics at each scheduled visit. Descriptive statistics include actual value, change from baseline and percent change from baseline at each scheduled visit.

Shift tables will be generated to summarize shifts from baseline categories to the worst post-baseline categories with directionality specified for any labs which could be reported in either direction (e.g. above ULN or below ULN).

Clinical laboratory tests with normal ranges will be classified as Low, Normal, and High. For these tests, abnormal values will be flagged in the listings with H when the value is higher than the upper limit of the reference ranges and with L when the value is lower than the lower limit of the reference ranges.

For hematology and chemistry labs, summary tables of potentially clinically significant abnormalities will also be provided.

All laboratory data will be presented in data listings. Separate listings will be included for those laboratory data collected from local labs such as LFTs. Out of range laboratory results will be identified in listings.

**Liver Function Tests (LFTs):** A listing will be generated for all patients with abnormal liver function tests as defined by ALT>3xULN, AST>3xULN and total bilirubin >2x ULN at any visit.

A tabular summary for LFTs will be generated to summarize the number and associated percentage of patient in each of the categories at any post-baseline visit:

- ALT>1 & ≤3, ALT>3 & ≤5, ALT>5 & ≤10, ALT>10 & ≤20, ALT>20xULN
- AST>1 & <3, AST>3&<5, AST>5& <10, AST>10 & <20, AST>20xULN
- ALT or AST>1 & ≤3, ALT or AST>3 & ≤5, ALT or AST>5 & ≤10, ALT or AST>10 & ≤20, AST or ALT>20xULN
- WNL, ALP>1.5xULN
- Total Bilirubin>1.5& ≤2, Total Bilirubin>2&≤3, Total Bilirubin>3& ≤5 and Total Bilirubin>5

eDISH plots of peak total bilirubin at any time versus peak ALT or AST at any time will also be presented.

For selected labs (e.g. ALT/ULN and AST/ULN), a table and figure of the values across the entire study will be generated by treatment sequence arms.

